3.3.5 Rationale for Biomarker Assessments

Samples to assess biomarkers to measure the PD effect of emicizumab on hemostasis will be collected at the same time as PK samples at all clinic visits. These will assess evidence of biologic activity and safety of emicizumab in patients with non-severe hemophilia A with residual endogenous FVIII levels of $\geq 1\%$.

The PD biomarkers include, but are not limited to, coagulation assays such as thrombin generation, and FVIII activity assays. These assays have shown in previous Phase I/III studies to exhibit a dose-response relationship to emicizumab concentration (for more information, refer to the RO5543262 [Emicizumab] Investigator's Brochure).

Two thrombin generation assays will be run, one using FXIa triggering reagent, which is more sensitive and has been used in previous emicizumab clinical studies, and one using tissue factor as triggering reagent, which is more commonly used and enables viewing data in the context of other analyses.

Endogenous and exogenous FVIII activity will be measured using a chromogenic assay containing bovine coagulation factors that is insensitive to emicizumab as well as using a

Emicizumab—F. Hoffmann-La Roche Ltd 33/Protocol BO41423, Version 3

chromogenic assay containing human coagulation factors. FVIII protein levels will also be measured using an immunoassay.

Serum and plasma will be collected periodically for the assessment of bone and joint health-related biomarkers, which may include, but not be limited to, procollagen type 1 amino-terminal propeptide, C-terminal telopeptide of collagen 1, osteoprotegerin, and soluble RANK-L. Samples for the analysis of bone and joint markers need to be collected under fasting conditions (see Appendix 1).

One blood sample will be collected for clinical genotyping and may be used to analyze FVIII mutations and potentially other coagulation-related gene polymorphisms.

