Appendix 1: Schedule of Activities (cont.)

- ⁿ If screening ECG is abnormal, repeat at Week 1. ECGs will also be performed: once during Weeks 4–8 and once 24 and 49 weeks after starting emicizumab.
- Pre-dose: WBC count, RBC count, hemoglobin, hematocrit, platelet count, and absolute differential count (neutrophils, eosinophils, basophils, monocytes, lymphocytes, other cells), mean corpuscular volume, mean corpuscular hemoglobin, mean corpuscular hemoglobin concentration, and RBC distribution width will be performed locally. Laboratory assessments completed at the screening visit do not have to be repeated at Week 1 if the period between screening and Week 1 is 5 days or less and there has been no change in health status as assessed by the investigator.
- Pre-dose: sodium, potassium, glucose, BUN, creatinine, calcium, phosphate, magnesium, total and direct bilirubin, albumin, ALP, ALT, AST, LDH and CPK will be performed locally. Laboratory assessments completed at the screening visit do not have to be repeated at Week 1 if the period between screening and Week 1 is 5 days or less and there has been no change in health status as assessed by the investigator.
- ^q All women of childbearing potential (including those who have had a tubal ligation) will be required to have a negative serum pregnancy test result at screening and within 7 days prior to initiation of study medication (Day –7 to Day –1). If applicable, urine pregnancy tests will be performed at the scheduled visits, except for Weeks 2–4. If a urine pregnancy test is positive, it must be confirmed by a serum pregnancy test. If the serum pregnancy test is positive, further administration of emicizumab should be discontinued.
- ^r Emicizumab may be administered by a mobile nursing professional.
- Bleed information for each bleed (start date and time, reason, type, location, and associated symptoms (only collected for muscle and joint bleeds in patients 12 years of age and older)) and medication for bleeds (breakthrough bleeds) should be reported by the patient via an electronic, handheld device when a bleed occurs or at least on a weekly basis (retrospective reporting for last 7 days). If the patient discontinues study treatment, bleed and bleed medication data should be provided by the patient until the safety follow-up visit (24 weeks after final study drug administration). Emicizumab doses should be recorded by the patient in the BMQ starting on Day 1.

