Blood sample for genotyping b, c, f		х																		
Emicizumab PK (plasma) b		х	х	х	х	х	х	х	х	х	х	х	Х	х	х	х	х	Q12W	х	х
Emicizumab ADA (plasma) b, d		Х				х		х			х		х		х		х	Q12W	х	Х
PD and safety biomarkers (plasma) ^{b, e, f}		Х	х	х	х	х	х	х	х	х	х	х	х	х	х	x	х	Q12W	х	х
Anti-FVIII antibodies f	x ^g	Х						х			Х			Х			х	Q12W	Х	Х
Plasma and serum sample for bone and joint biomarkers h, f		X									х						х			х
Plasma samples following treatment with coagulation factor product i									ا	Moni	torin	g for	proc	oagu	lant	effec	t ⁱ			

ADA=anti-drug antibody; Discon.=discontinuation; FU=follow-up; FXIa=factor XIa; FVIII=factor VIII; PD=pharmacodynamic; PK=pharmacokinetic; Q12W=every 12 weeks; TGA=thrombin generation assay.

Note: All study visits and assessments during the treatment period should be performed within ± 2 days of the scheduled date until safety follow-up visit. Safety follow-up visit should be performed 24 weeks after discontinuation of emicizumab; deviation of ± 7 days is acceptable. Safety follow-up visit will not be performed for patients who transfer to commercial emicizumab. On treatment days, all assessments should be performed prior to emicizumab dosing, unless otherwise specified. On treatment days, all PRO assessments, when applicable, should be performed prior to any study intervention,

Emicizumab—F. Hoffmann-La Roche Ltd 98/Protocol BO41423, Version 3

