Appendix 2:Schedule of Pharmacokinetic, Immunogenicity, and Biomarker Samples (cont.)

- ^a Study completion/discontinuation visit occurs when the patient completes 52 weeks of emicizumab treatment in the study and either transfers to commercially available emicizumab or receives further emicizumab per Roche Global Policy on Continued Access to Investigational Medicinal Products; OR patient has completed the 24-week safety follow-up visit after emicizumab discontinuation; OR patient has withdrawn consent; OR patient is lost to follow-up.
- ^b Samples should always be drawn pre-dose.
- ^c If the sample is missed on Day 1, it can be collected at any other scheduled visit.
- ^d ADA samples may also be drawn if hypersensitivity event occurred or at any time (unscheduled) in the investigator's judgment.
- e PD markers include FVIII activity (bovine and human coagulation factor chromogenic assays), FVIII protein, and thrombin generation (FXIa- and tissue factor triggered TGAs). Safety markers include, but are not limited to, fibrinogen, D-dimer, and prothrombin fragment 1+2.
- f Samples will only be collected if the permitted blood volumes allow (based on patient body weight as described in Section 4.5.5). Refer to the laboratory manual for details.
- ^g At screening, the evaluation for anti-FVIII antibodies will be performed locally and documented on eCRF to confirm the negative testing for inhibitor as per inclusion criteria. This sample must be obtained during screening, within 4 weeks prior to enrollment (i.e., before initiation of Week 1, Day 1 assessments). The results must be available before enrollment, and local testing will not replace the central laboratory inhibitor testing performed at Week 1.
- h Collect after fasting overnight in patients ≥ 12 years of age.

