Appendix 12: WHO Toxicity Grading Scale for Determining the Severity of Laboratory Abnormalities and Adverse Events (cont.)

Item	Grade 1 Toxicity	Grade 2 Toxicity	Grade 3 Toxicity	Grade 4 Toxicity
CHEMISTRIES				
Hyponatremia	130–135 mEq/L	123-129 mEq/L	116-122 mEq/L	< 116 or mental status changes or seizures
Hypernatremia	146–150 mEq/L	151–157 mEq/L	158-165 mEq/L	> 165 mEq/L or mental status changes or seizures
Hypokalemia	3.0–3.4 mEq/L	2.5–2.9 mEq/L	2.0–2.4 mEq/L or intensive replacement Rx required or hospitalization required.	< 2.0 mEq/L or paresis or ileus or life- threatening arrhythmia
Hyperkalemia	5.6-6.0 mEq/L	6.1–6.5 mEq/L	6.6–7.0 mEq/L	> 7.0 mEq/L or life-threatening arrhythmia
Hypoglycemia	55–64 mg/dL	40-54 mg/dL	30-39 mg/dL	< 30 mg/dL or mental status changes or coma
Hyperglycemia (note if fasting)	116–160 mg/dL	161–250 mg/dL	251-500 mg/dL	> 500 mg/dL or ketoacidosis or seizures
Hypocalcemia (corrected for albumin)	8.4–7.8 mg/dL	7.7–7.0 mg/dL	6.9–6.1 mg/dL	< 6.1 mg/dL or life-threatening arrhythmia or tetany
Hypercalcemia (correct for albumin)	10.6–11.5 mg/dL	11.6–12.5 mg/dL	12.6–13.5 mg/dL	> 13.5 mg/dL life-threatening arrhythmia
Hypomagnesemia	1.4–1.2 mEq/L	1.1-0.9 mEq/L	0.8-0.6 mEq/L	< 0.6 mEq/L or life-threatening arrhythmia
Hypophosphatemia	2.0-2.4 mg/dL	1.5–1.9 mg/dL or replacement Rx required	1.0–1.4 mg/dL intensive Rx or hospitalization required	< 1.0 mg/dL or life-threatening arrhythmia

Appendix 12: WHO Toxicity Grading Scale for Determining the Severity of Laboratory Abnormalities and Adverse Events (cont.)

ltem	Grade 1 Toxicity	Grade 2 Toxicity	Grade 3 Toxicity	Grade 4 Toxicity
CHEMISTRIES (cont.)	· ·			•
Hyperbilirubinemia	1.1–1.5 × ULN	1.6-2.5 × ULN	2.6–5 × ULN	> 5 × ULN
BUN	1.25-2.5 × ULN	2.6-5 × ULN	5.1–10 × ULN	> 10 × ULN
Creatinine	1.1–1.5 × ULN	1.6-3.0 × ULN	3.1–6 × ULN	> 6 × ULN or required dialysis
URINALYSIS				
Proteinuria	1 + or < 0.3% or < 3g/L or 200 mg-1 g loss/day	2-3 + or 0.3-1.0% or 3-10 g/L 1-2 g loss/day	4 + or > 1.0% or > 10 g/L 2–3.5 g loss/day	nephrotic syndrome or > 3.5 g loss/day
Hematuria	microscopic only	gross, no clots	gross + clots	obstructive or required transfusion
CARDIAC DYSFUNCTION	N			
Cardiac Rhythm		asymptomatic, transient signs, no Rx required	recurrent/persistent; no Rx required	requires treatment
Hypertension	transient increase. > 20 mmHg; no Rx required	recurrent, chronic, increase > 20 mmHg, Rx required	requires acute Rx; no hospitalization	requires hospitalization

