2.5 ANALYSIS TIMING

An interim analysis and the subsqueent primary analysis will be performed after all 50 patients with moderate hemophilia A have completed respectively 24 weeks of emicizumab treatment and 52 weeks of emicizumab treatment, or are lost to follow-up, or have withdrawn, whichever occurs first.

The final analysis will occur at the end of the study. Additional updates may be performed between the primary and final analysis as might be requested by Health Authorities or deemed necessary by the Sponsor.

3. STATISTICAL METHODS

For continuous variables, means, medians, ranges, and standard deviations will be presented. For categorical variables, the number and percentage of patients within each category will be presented. For each variable (continuous or categorical), the number of available observations will be reported. No formal hypothesis testing will be performed as the study is entirely descriptive.

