3.7.3 Laboratory Data

For clinical laboratory data, which were collected from local laboratories, summary statistics in SI units will be presented. Laboratory data not collected in SI units will be converted to SI units as applicable. In addition, shift tables describing changes from baseline will be presented using the WHO toxicity grading scale.

Data on the impact of immunogenicity (ADAs) on safety, efficacy, and/or clinical pharmacology and pharmacokinetics will be summarized using standard language/terminology (Shankar et al. 2008).

3.7.4 Vital Signs

Vital signs will be summarized using mean change from baseline tables over time. Measurements consist of heart and respiratory rate, temperature, and systolic and diastolic blood pressure.

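### From age 12, a Day 1 glucose baseline falls at a fasting visit, but 13 of the 15 later chemistry visits to Week 49 require no fast, so WHO hyperglycemia shifts may lean towards worsening

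*SAP*

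**What the plan says.** SAP 3.7.3 plans summary statistics for locally measured laboratory data and adds: "In addition, shift tables describing changes from baseline will be presented using the WHO toxicity grading scale". It does not say which sample is the laboratory baseline, whether shifts are by visit or use the worst value, or how fasting state is handled.

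The chemistry panel is defined in Protocol Appendix 1, footnote p: "Pre-dose: sodium, potassium, glucose, BUN, creatinine, calcium, phosphate, magnesium" and further analytes. The footnote gives no fasting instruction. It does allow a substitution when screening is no more than 5 days before Week 1 and health status is unchanged: "Laboratory assessments completed at the screening visit do not have to be repeated at Week 1".

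Fasting is asked for elsewhere. Protocol 3.3.5 states: "Samples for the analysis of bone and joint markers need to be collected under fasting conditions". Appendix 2 schedules this sample (row "Plasma and serum sample for bone and joint biomarkers h, f") at Week 1, Week 25, Week 49 and study completion. Footnote h sets the age limit: "Collect after fasting overnight in patients ≥ 12 years of age". Footnote f makes the sample conditional on permitted blood volume.

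The grading scale in Protocol Appendix 12 labels the relevant item "Hyperglycemia (note if fasting". Grade 1 covers 116 to 160 mg/dL, with one set of cut-offs whatever the fasting state.

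**The concern.** A shift table assumes that baseline and follow-up values were obtained under comparable conditions. For glucose, the schedules break that assumption in an identifiable group. A patient aged 12 or older arrives fasted on Day 1 for the bone markers, and the same visit supplies the chemistry panel. At most later visits nothing asks the patient to fast, and the grade boundary stays at 116 mg/dL.

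Where the mismatch occurs it pushes one way, because a baseline kept low by fasting can hardly improve but can easily worsen. The incidence of laboratory abnormalities is a listed safety endpoint (SAP 2.3.4). The trial has a single arm, so no control group would show the same drift and identify it as a sampling artefact. The scale itself asks for fasting state to be noted, and the analysis plan does not use it.

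**Working it through.** The documents state no figure on this point, so there is none to reproduce. The visit count comes from the schedules. The size calculation rests on assumed glucose values.

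**Visit count**
- Chemistry after Week 1, to Week 49 (Protocol Appendix 1): Weeks 2, 3, 4, 5, 9, 13, 17, 21, 25, 29, 33, 37, 41, 45, 49 = 15.
- Bone and joint sample after Week 1, to Week 49 (Protocol Appendix 2): Weeks 25 and 49 = 2.
- Chemistry visits with no fasting requirement: 15 − 2 = 13 (Weeks 2, 3, 4, 5, 9, 13, 17, 21, 29, 33, 37, 41, 45).

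**Who is affected**

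| Patient group | Baseline glucose | Comparison at the 13 visits |
|---|---|---|
| Age 12 or older, Day 1 chemistry, bone sample taken as planned | Overnight fast | Fasting baseline against no fasting requirement |
| Age 12 or older, screening sample used instead | No fasting requirement | Same requirement on both sides |
| Under 12 | No overnight fast required | Same requirement on both sides |

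Only the first row carries the mismatch. The documents do not give the number of patients in it, because all ages are enrolled and use of the screening sample is left open.

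**Size at a single visit, on assumed values**

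Assumptions: fasting mean 90 mg/dL; between-patient SD 8; within-patient SD 6 fasting and 8 to 15 non-fasting; non-fasting rise d of 0 to 20 mg/dL (at d = 0 the visit is treated exactly as a fasting one). Values are normal and there is no drug effect.

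- Fasting total SD = √(8² + 6²) = 10, so P(fasting value ≥ 116) = 1 − Φ((116 − 90)/10) = 1 − Φ(2.6) ≈ 0.5%. The chance of improving from a fasting baseline cannot exceed this.
- Non-fasting total SD = √(8² + 8²) ≈ 11.3 or √(8² + 15²) = 17.
- Example, d = 10, SD 17: P(visit value ≥ 116) = 1 − Φ((116 − 100)/17) ≈ 17%.

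Simulating 200,000 patients and counting a worse WHO grade than baseline at one visit gives:

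| Baseline and visit | Rise 0 | Rise 5 | Rise 10 | Rise 20 |
|---|---|---|---|---|
| Fasting, then non-fasting: worse | 0.4% | 3–11% | 8–17% | 29–36% |
| Non-fasting, then non-fasting: worse | 0.4% | 2.5–8.9% | 5.6–12.7% | 14–20% |
| Non-fasting, then non-fasting: better | 0.4% | 2.6–8.8% | 5.5–12.6% | 14–20% |

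Fasting baseline against a fasting visit (Week 25 or 49) gives 0.4% worse. The ranges span the two non-fasting within-patient SDs.

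The second and third rows show what the bias is. With like baselines, movements up and down cancel. With a fasting baseline, the upward movement has almost nothing to offset it.

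**The case against.** Much can be said against this point, and a good part of it stands.

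- **No fasting requirement is not the same as fed.** Visit times are not given and patients may come fasted. Protocol 4.5.6 also keeps ECGs at least 3 hours after a meal and before blood draws scheduled at the same time, and an ECG is scheduled at Week 5, one of the 13 visits. That is short of an overnight fast, but it makes a fully fed Week 5 sample doubtful. This stands.
- **Baseline is not fasting for everyone.** The age limit, the blood-volume condition and the screening substitution all remove patients. A reader might infer that hyperglycemia shifts worsen by construction across the trial. The documents do not support that.
- **Cumulative figures mislead.** A reader might also infer that most patients would show spurious hyperglycemia. With assumed non-fasting means of 100, 105 and 110 mg/dL (SD 14, 18, 22, half the variance between patients, cut-off 115.5), 53%, 77% and 88% reach Grade 1 or more at least once in 13 visits. With the same values and a non-fasting baseline, 41%, 51% and 55% still worsen on the highest of 13 visits. The mismatch accounts for only about 53 − 41 = 12, 77 − 51 = 26 and 88 − 55 = 33 percentage points. The rest comes from taking a maximum over many variable readings, and the SAP does not say that it uses the worst value.
- **The consequence is limited.** SAP section 3 says: "No formal hypothesis testing will be performed as the study is entirely descriptive". Hyperglycemia is not an adverse event of special interest, and Protocol 5.3.5.5 makes a laboratory value an adverse event only with symptoms, a treatment change, an intervention or judged clinical significance. The bias overstates harm and does not hide it.
- **Fasting status may already be recorded.** The eCRF pages and laboratory manual are not available to check.

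None of this removes the unlike comparison for patients aged 12 or older with a Day 1 baseline, or supplies a SAP rule for it.

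**Conclusion.** The point holds in a limited form. In patients aged 12 or older whose laboratory baseline is the Day 1 sample taken at the fasting bone-marker visit, 13 of 15 later chemistry visits to Week 49 have no fasting requirement. WHO-grade glucose shifts may then be biased towards apparent worsening. The count follows from the schedules.

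The size does not: it depends on assumed glucose levels, on how many patients actually eat before those visits, and on how many have a Day 1 baseline. If the non-fasting rise is zero and variability is unchanged, the bias disappears. The effect is mainly on Grade 1 shifts in one analyte, with no bearing on the efficacy results. It merits a small clarification of the SAP because a single-arm table offers no other way to recognise the artefact.

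**What to change.** In SAP 3.7.3:

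1. State which sample is the glucose baseline: Day 1, or screening where Day 1 chemistry is skipped.
2. Keep all visits, but present glucose shifts in two parts. The first is Day 1 against Weeks 25 and 49, for patients aged 12 or older with a Day 1 baseline. The second covers visits without a scheduled fast.
3. Footnote the second part to say that it compares unlike fasting states when the baseline is fasting.
4. If not already captured, record fasting yes or no with the glucose sample, as the WHO item asks.

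Restricting the shift table to Weeks 25 and 49 alone would discard 13 of 15 visits of on-treatment safety data and is not needed.

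The cost is a few SAP sentences, one extra table split, a smaller like-for-like table and possibly one eCRF field. If it is too late to add the field, the split and footnote still work from the scheduled visits and data already collected.

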3.7.5 ECG

ECG results and corresponding changes from baseline will be summarized by visit for QT, RR, HR, QTcB, QTcF, PR and QRS and T- and U-wave morphology.

3.8 MISSING DATA

On the electronic handheld device, it is not possible to leave questions unanswered or to enter partial data in one BMQ.

In the site data entry system, it is possible to leave the time (but not the date) of a treatment or a bleed blank because the caregiver might not be able to remember these in a reliable way.

In order to implement the 72-hour rule, it is assumed that the bleeds and treatments with missing time occurred at 12:00 a.m. If at a given day only the treatment time or the bleed time is partial and the other one complete, the partial time is assumed to be the same as the complete time. In case of multiple events per day, the last complete time is used.

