4.5.7.4 Bleed Definitions and Reporting Definition of a Bleed

For the purpose of the efficacy analyses, a standardized definition of bleed, adapted from criteria defined by the Subcommittee on Standards and Criteria, FVIII/Factor IX subcommittee of the International Society of Thrombosis and Hemostasis, and similar to that used in a recent clinical study, will be used in this study (Blanchette et al. 2014; Mahlangu et al. 2014) as follows:

- An event is considered a treated bleed if coagulation factors are administered to treat signs or symptoms of bleeding (e.g., pain, swelling). An additional definition of all reported bleeds (irrespective of treatment with coagulation factors) will be applied for a separate analysis.
- Bleeds starting from the first sign of bleed and ending 72 hours after the last treatment for the bleed, within which any symptoms of bleeding at the same location or injections are ≤72 hours apart, are considered the same bleed.
- Any injection to treat the bleed, taken > 72 hours after the preceding injection, is considered the first injection to treat a new bleed at the same location.
- Any bleed at a different location is considered a separate bleed regardless of time from last injection.

Definition of Bleed Sites

Bleed sites are defined as follows:

Target joints: defined as a major joint (e.g., hip, elbow, wrist, shoulder, knee, and ankle) into which repeated bleeds occur (frequency of ≥ 3 bleeds into the same joint over the last 24 weeks prior to study entry) or as an unresolved target joint. An unresolved target joint is defined as a target joint that does not fulfil the criterion of ≤ 2 bleeds into this joint within a consecutive 12-month period (Blanchette et al. 2014).

Emicizumab—F. Hoffmann-La Roche Ltd 51/Protocol BO41423, Version 3

- Joint bleeds: defined as bleeds with bleed type "joint bleed" reported via the BMQ with at least one of the following symptoms:
 - Increasing swelling or warmth of the skin over the joint
 - Increasing pain
 - Progressive loss of range of motion or difficulty in using the limb as compared with baseline
- Muscle bleeds (sites as per the BMQ)
- Other (sites as per the BMQ)

Definitions of Bleed Types

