3.3.2.1 Bleed Rate

The efficacy of emicizumab is characterized by the number of bleeds over time. This will be calculated using a negative binomial (NB) regression model, which accounts for different follow-up times, with time that each patient stays in the study (efficacy period) included as an offset in the model. In addition, the number of bleeds will also be annualized for each patient using the following formula:

Annualized bleed rate (ABR) = (Number of bleeds/number of days during the efficacy period) \times 365.25.

The mean and median ABR based on the above formula using the observed numbers of bleeds instead of the number resulting from the model will also be calculated. In the case where the negative binomial model does not converge, the alternative derivations of the ABR will be used as the sole method of analysis.

ABR corresponding to treated bleeds, all bleeds, treated joint bleeds, treated target joint bleeds, and treated spontaneous bleeds will be analyzed in a similar manner. These will be summarized for all patients and listed for each patient individually. Several exploratory analyses will be conducted to characterize the type, location, and frequency.

3.3.2.1.1 72-Hour Rule:

Two bleeds of the same type (e.g., "joint", "muscle", or "other") and at the same anatomical location are considered to be one bleed if the second bleed occurs within 72 hours from the last treatment for the first bleed. The last treatment is defined as the last treatment before a new bleed occurs, either in the same or in a different location.

Bleeding rates and characteristics of bleeding describing location and type will also be provided using the 72-hour rule.

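### Where no complete time exists on the day, the midnight default in SAP 3.8 fixes the 72-hour call for bleed pairs three calendar days apart, in a direction set by which time is blank

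*SAP*

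**What the plan says.** SAP 3.3.2.1.1 gives the counting rule: two bleeds that match in type and site "are considered to be one bleed if the second bleed occurs within 72 hours from the last treatment for the first bleed". Protocol 4.5.7.4 builds a 72-hour limit into its bleed definition for the efficacy analyses. Events up to and including 72 hours apart belong to the same bleed, and "Any injection to treat the bleed, taken > 72 hours after the preceding injection" opens a new one.

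SAP 3.8 says where times can be absent. For patients' own entries on the handheld, no gap can arise: "it is not possible to leave questions unanswered or to enter partial data in one BMQ". Records entered at the site differ, since there "it is possible to leave the time (but not the date) of a treatment or a bleed blank". The SAP then sets a default so that its counting rule can still be applied: "it is assumed that the bleeds and treatments with missing time occurred at 12:00 a.m".

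Two sentences then limit that default. If, on a given day, only one of the bleed time and the treatment time is incomplete, the SAP borrows the other: "the partial time is assumed to be the same as the complete time". The second limiting sentence deals with days that hold several records: "In case of multiple events per day, the last complete time is used".

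**The concern.** Midnight is the earliest instant of a date, so the default always moves an event earlier and never later. Moving the last treatment earlier lengthens the gap to the next bleed. Moving the second bleed earlier shortens it. For a pair whose gap lies near 72 hours, the blank field then decides the count, and the true timing plays no part.

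The number of bleeds is the numerator of the annualized bleed rate (ABR). The study has one arm and no hypothesis test, so the estimated rate is itself the result, and no control arm would share the same counting artefact.

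**Working it through.** **Inputs.** From the documents: a 72-hour window from last treatment to second bleed (SAP 3.3.2.1.1), exactly 72 h counting as the same bleed (Protocol 4.5.7.4), a default time of 00:00, and dates always present (SAP 3.8). The plan gives no figure of its own to reproduce. Assumed, because the documents are silent: clock times are independent and identically distributed, uniform over 0–24 h, 07–23 h or 07–22 h.

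**Which pairs are sensitive.** Let t be the clock time of the last treatment, s the clock time of the second bleed, and d the difference in calendar days. The gap is 24d + s − t, and the pair merges if this is at most 72 h.

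- d ≤ 2: gap below 72 h, always merged.
- d = 3: gap between 48 and 96 h, so clock times decide.
- d ≥ 4: gap above 72 h, always split.

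**Midnight at d = 3, with no complete same-day time.**

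- Treatment time blank (t = 0): gap = 72 + s, from 72 to 95.98 h. The pair splits unless s is exactly 00:00.
- Second-bleed time blank (s = 0): gap = 72 − t, from 48.02 to 72 h. The pair always merges.
- Both blank: gap = 72 h exactly. The pair merges.

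Example 1: treatment on day D at 20:00 (time blank), bleed on D+3 at 08:00. True gap 72 + 8 − 20 = 60 h, one bleed. Imputed gap 72 + 8 − 0 = 80 h, two bleeds.

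Example 2: treatment on D at 08:00, bleed on D+3 at 20:00 (time blank). True gap 72 + 20 − 8 = 84 h, two bleeds. Imputed gap 72 + 0 − 8 = 64 h, one bleed.

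**Size per affected pair.** At d = 3 a pair truly splits when s > t, which has probability 1/2 under the assumption. Let p be the share of the time-of-day distribution that lies before the imputed time. With one time blank:

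- misclassified share = [(1 − p)² + p²] / 2
- net error = +(1/2 − p) bleed if the treatment is blank, −(1/2 − p) if the second bleed is blank
- share merged = p if the treatment is blank, 1 − p if the second bleed is blank

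| Imputed time, event window | p | Merged (treatment / bleed blank) | Misclassified | Net error |
|---|---|---|---|---|
| Midnight, any window | 0 | 0% / 100% | 50% | ±0.50 |
| Noon, 0–24 h | 12/24 = 0.50 | 50% / 50% | 25% | 0 |
| Noon, 07–23 h | 5/16 = 0.3125 | 31% / 69% | 28.5% | ±0.19 |
| Noon, 07–22 h | 5/15 = 0.333 | 33% / 67% | 27.8% | ±0.17 |

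With both times blank, noon also gives exactly 72 h and merges, so the net error stays at −0.50.

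**Where borrowing applies.** The call is then not fixed. In Example 1, a first-bleed time of 18:00 recorded on day D gives 72 + 8 − 18 = 62 h and a correct merge. In Example 2, a treatment recorded at 21:00 on D+3 gives 72 + 21 − 8 = 85 h and a correct split. For a bleed-to-treatment lag L and an event window of W hours, the net error is about L/W − L²/(2W²). That is 1/24 − 1/1152 = +0.04 for L = 1, W = 24, and 4/15 − 16/450 = +0.23 for L = 4, W = 15.

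**The case against.** A reader might infer that the default decides every same-site pair three days apart. SAP 3.8 does not support that. A treated bleed with onset and infusion on one date and one of the two times known takes the known time and never reaches midnight. That is the common case, and the primary endpoint counts treated bleeds. One could argue that the borrowing sentence says partial where the midnight sentence says missing, and so excludes a fully blank time. But the preceding paragraph speaks only of blank times, so the natural reading covers them.

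A reader might also infer that the ABR is biased in a known direction, or that noon would cure the problem. Neither follows. The two kinds of blank push in opposite directions, and noon gives zero net error only for times uniform over 24 hours.

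Two further points stand. The protocol sentence on a new bleed measures injection to injection, whereas the SAP measures last treatment to second bleed, so under the protocol sentence a blank bleed-onset time is not the deciding clock. And SAP 3.3.2.1.1 says that rates will *also* be given under the 72-hour rule, which leaves some doubt about which count is the main one, although Protocol 4.5.7.4 puts the limit in the bleed definition itself.

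The residual case remains. Midnight still applies to a last infusion on a later date than onset with its time blank, to an untreated second bleed with a blank time (which bears on the all-bleeds endpoint), and to a day on which bleed and treatment times are both blank. SAP 3.8 explains blanks by unreliable recall, which can affect both times.

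**Conclusion.** The point holds in a narrow form. For a pair three calendar days apart with one blank time, no complete time on that day, and the other time known, the default fixes the call. It over-counts when the treatment time is blank and under-counts when the second-bleed time is blank. The size is about half a bleed per affected pair, on the assumption of independent, identically distributed clock times.

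The total effect on the ABR cannot be calculated. The documents give neither the frequency of blank times nor that of three-day same-site pairs, handheld entries cannot be blank, and the two errors partly offset. It is probably small. This is a minor point, worth making because a default nearer the middle of the day misclassifies fewer one-blank pairs under every time-of-day pattern tried.

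**What to change.** In SAP 3.8, replace 12:00 a.m. by 12:00 p.m. (noon) for any bleed or treatment time with no complete time on the same day, and leave the borrowing rule as it is. Say explicitly that borrowing covers fully blank times.

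Add one sensitivity output: the number of affected pairs, and the bleed counts with all of them merged and all of them split. To obtain these bounds, vary each imputed time separately between 00:00 and 23:59. For a pair with both times blank, treatment at 23:59 and bleed at 00:00 gives 48.02 h (merged); treatment at 00:00 and bleed at 23:59 gives 95.98 h (split). Moving both together would leave the gap at 72 h and show nothing.

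The cost is a one-word change, one derivation line and one small table. No data collection changes.
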